4.3 Derived variables

Both death and stent thrombosis will be classified per the ARC criteria (Cutlip et al., 2007). Myocardial Infarction will be defined per the 2007 Universal definition (Thygesen et al., 2007). Stroke will be defined as a physician-determined focal neurological deficit of cerebrovascular origin that persists for at least 24 hours. Unplanned revascularization is defined as any revascularization (PCI/CABG) that is not staged. MACE is the composite occurrence of all-cause death, stroke, MI or unplanned revascularization. Total follow-up time for all patients will be defined as time from index PCI until time of death, last contact, or 365 days whichever comes first.

5 Study Methods

5.1 Study Design

Study B020 is designed as a retrospective cohort study evaluating data for patients presenting with ACS managed with a PCI from 8 academic centers in the US from 01 January 2010 to 30 June 2013, with any follow-up data available for analysis. The centers include: Mount Sinai Medical Center, Intermountain Heart Institute, Duke University, Cleveland Clinic Foundation, University of Pittsburgh, University of Minnesota, Christiana Health Care and Aurora Research Institute. This study will evaluate the comparative effectiveness and economics of a treatment strategy initiating prasugrel relative to clopidogrel in approximately 8,600 patients (minimum 4,300 receiving prasugrel) in a usual care environment from academic centers in the US. These academic centers maintain institutional databases related to baseline characteristics, procedural characteristics, and clinical and economic outcomes during and following index hospitalization of patients with ACS undergoing PCI.

The participating academic centers will run a query in their ACS-PCI database to identify all patients who received prasugrel or clopidogrel between 01 January 2010 and 30 June 2013. The study period was selected based on the approval and availability of prasugrel in the US market at the end of 2009 and by the need for a study with a minimum 90-day follow-up in this population. The primary endpoint of the study will be at 90 days from index PCI; at this point in therapy, the adherence rate is expected to continue to be high while the switching rate is expected to be low ($\leq 10\%$). Figure 1 illustrates the study time periods

[figure not shown]

Figure 1 Study B020 design for patients with ACS managed with PCI and treated with prasugrel or clopidogrel between 01 January 2010 and 30 June 2013.

5.2 Data Source

Each of the academic centers selected to participate in Study B020 will provide information on the patterns of antiplatelet use for ACS patients undergoing PCI and specifically their volumes for the period from 01 January 2010 to 30 June 2013 through a site selection questionnaire. Each of the participating centers maintains high quality institutional databases of both in-hospital and post-discharge follow-up events. The data in these sets are derived primarily from the NCDR CathPCI database while the post-discharge follow-up data is physician-determined diagnoses at time of hospitalization as described in Section 4.3. The index hospital data is collected at most sites according to the definitions used in CathPCI registry data collection form. No adjudication of the data will be performed. These databases do not typically include prescriptions, adherence, or outpatient encounters. This project will extract data from the participating centers using extraction sheets with standardized definitions. Extracted data will be entered in a Core Study Dataset for data analyses.

5.3 Study Populations

Inclusion criteria:

1. At least 18 years of age at time of index PCI.
2. Diagnosed with ACS (STEMI, NSTEMI, UA) and managed by PCI with stent implantation during the index hospitalization between 01 January 2010 and 30 June 2013
3. Treatment with prasugrel or clopidogrel during index hospitalization either prior to, or during the peri-procedural period (as defined below)

Populations of Interest:

1. All ACS-PCI patients
2. ACS-PCI patients with no prior TIA or stroke
3. ACS-PCI patients with no prior history of TIA or stroke and are:
 - i. <75 years of age, or
 - ii. ≥ 75 years of age with diabetes mellitus or a prior history of MI
2. Diabetes mellitus
3. NSTEMI/UA
4. STEMI

5. Gender
6. Presence or absence of multivessel disease
7. Presence or absence of chronic kidney disease, defined as an estimated glomerular filtration rate < 60 ml/min/1.73m²

6 Plan of Analysis

6.1 Methods

Primary Objective

The exposure groups for the primary analysis will be defined as those patients receiving prasugrel or clopidogrel at the time of PCI (i.e. loaded peri-procedurally or currently taking in the absence of a load). All patients will be assigned to one of these mutually exclusive groups irrespective of medication administered at discharge. Patients administered both medications at the time of PCI will be excluded for any comparative analyses of treatments.

For descriptive purposes, baseline clinical (including laboratory evaluations) and demographic and procedural characteristics will be compared between groups using student's t-test and chi-square test or Fisher's exact test for continuous and categorical variables, respectively.

In-hospital (that is, post-procedural) outcomes will be assessed by comparing the proportion of post-procedural events between prasugrel and clopidogrel groups. These crude unadjusted binary proportions will be performed using a Chi-square test between groups.

The primary endpoint of interest is the first occurrence of MACE within 90 days from date of index PCI. For purposes of this primary analysis, event-free patients will be censored at 90 days or last contact, whichever comes first. For the primary outcome of interest, the crude unadjusted 90-day rates of MACE will be calculated for each group using the *Kaplan-Meier method, also including index hospital events*. Crude rates will be compared between groups using the logrank test (Kalbfleisch et al. 1980; Prentice et al. 1978).

To evaluate the adjusted associations between treatment group (therapy initiation with prasugrel versus clopidogrel) and the primary MACE outcome, hazard ratios will be calculated using Cox proportional hazards regression that are stratified by the propensity to receive either prasugrel or clopidogrel.

Propensity scores will be calculated using a multivariable logistic regression model with the dependent outcome as treatment initiation with prasugrel (versus clopidogrel). In addition to age, and gender, this model will include all baseline covariates demonstrating significant differences ($p < 0.05$) between groups. Additional variables for which there is consensus that may be related to either the outcome or exposure will also be included as covariates, even in the absence of significant baseline differences between groups. From this logistic regression model, each observation will be assigned a predicted probability for prasugrel treatment. Baseline characteristics including calculated propensity score will be reviewed to better understand the data and specified analyses plan for the outcomes (stratification, matching, IPW, and etc) will be finalized and documented prior to any actual analyses on the outcomes. The distribution of propensity scores for the entire cohort and each treatment group will be visually examined. Mutually exclusive strata will then be generated based on the propensity scores for the entire cohort, a process which will be blinded to any outcome data in order to avoid bias in selection. The number of strata and their respective cut-points will not be defined *a priori* but will be based on fulfilling the following criteria:

1. Sufficient number of strata to ensure adequate bias adjustment (i.e. at least 5 strata) [Rosenbaum et al., 1984];
2. Sufficient proportion of prasugrel and clopidogrel patients (at least 3%) within each stratum to allow reliable risk estimation [D'Agostino et al., circulation 2007];
3. Adequate balance in baseline covariates will be assessed by calculating the standardized differences between exposure groups within strata for the following variables: age, gender, serum creatinine, serum hemoglobin and prevalence of DM. A standardized difference exceeding 10% will be considered as inadequate bias adjustment..
4. Individuals with an extremely high or low propensity for prasugrel, defined as propensity scores exceeding the 95th or below the 5th percentile for the

entire cohort, may be removed from the analysis of the primary MACE endpoint (i.e. trimming).

The adjusted associations between exposure groups and the primary MACE outcome will then be calculated using Cox proportional hazards regression. This model will include the following two covariates: exposure group (prasugrel versus clopidogrel) and study center, with propensity group entered as a stratification variable.

The following sensitivity analyses for the primary MACE outcome will also be performed:

1. Covariate adjustment. Hazard ratios for the primary MACE outcome associated with prasugrel versus clopidogrel treatment will be generated using a fully-fitted Cox proportional hazards regression model. In addition to age, , gender and study center, this model will include all baseline covariates demonstrating significant differences ($p < 0.05$) between groups. Other baseline variables that may be plausibly related to the primary outcome will also be included: BMI, race, diabetes mellitus, serum creatinine, hemoglobin, prior MI, prior CHF, prior PAD, prior cerebrovascular disease, multivessel disease, CAD presentation (unstable angina vs. nstemi vs. stemi), current smoking, number of stents implanted, stent type and stent diameter (maximum). A second covariate-adjusted model will be generated using forward stepwise regression with treatment forced in first.

2. Propensity matching: A 1:1 matched cohort will be derived from the overall sample using the propensity scores as described above. Matches will be generated using nearest neighbour matching without replacement (Austin 2011).

3. Equipoise Analysis: From the overall cohort, an 'equipoise' subgroup will be derived that includes all patients with preference scores ranging between 0.4 – 0.6. These patients are assumed to have a reasonable high probability of being assigned to either treatment (Walker et al., 2013).

4. Inverse Probability Weight Analysis: Inverse probability weights (IPW) will be derived for all observations using the propensity scores. Observations with propensity scores exceeding the 95th percentile or below the 5th percentile for the

entire cohort will be excluded (trimmed) for purposes of this specific analysis. After trimming regression analyses will be performed using these weights.

5. A sensitivity analysis for the primary MACE outcome will be performed by defining exposure groups as those patients receiving the same medication at the time of PCI and at discharge. For purposes of this sensitivity analysis, dependent outcome will be restricted to out-of hospital MACE and will exclude those patients with in-hospital death.

Secondary Objectives

Analyses for the secondary clinical outcomes, including subgroups, will be performed using propensity score with stratification as outlined above with covariate adjustment as a sensitivity analysis.

Note: Section 6.2 Economic Outcomes Analyses (including Sections 6.2.1 Unadjusted Outcomes Analyses and 6.2.2 Adjusted Outcomes Analyses) will be contained in *Addendum 1: Economic Outcomes Analyses*. References in the economic section will be added to reference list along with Addendum 1.

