3.3.3. Study Populations

Inclusion criteria: Adult patients:

1. At least 18 years of age
2. Diagnosed with ACS (STEMI, NSTEMI, UA) and managed by PCI during index hospitalization between 01 January 2010 and 30 June 2013
3. Initiated use of prasugrel or clopidogrel during index hospitalization either prior to, during, or in the peri-procedural period (as defined below) of the index PCI and were discharged on the same medication as initiated during the peri-procedural period. Patients initiated on 1 agent prior to PCI and then switched to the other agent in the peri-procedural period (prior to, during, or ≤ 3 hours post-procedure) will also be eligible for analysis.

Subgroups of interest:

1. ACS-PCI patients with no prior TIA or stroke
2. ACS-PCI patients with no prior history of TIA or stroke and are:
 - a. <75 years of age, or
 - b. If ≥ 75 years of age, have diabetes mellitus or a prior history of MI
3. Age ≥ 75 years
4. Diabetes mellitus

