6.5 Multiplicity

The primary endpoint of interest in the present study is 90-day MACE, for which a Type I error rate of 0.05 will be used. All other endpoints are secondary and therefore no multiplicity adjustments will be performed.

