6.8 Sample Size and Power Considerations

Study B020 is designed to assess the difference in MACE associated with prasugrel versus clopidogrel in patients presenting with ACS managed with a PCI from academic centers in the US from 01 January 2010 to 30 June 2013. Data from the Premier study and from TRANSLATE-ACS have suggested that the MACE rate at 90 days will be approximately 8.0%. Using 8.0% as the control rate, it is expected that the relative reduction with prasugrel will be 20% lower than with clopidogrel (hazard ratio 0.80). To achieve 80% power with an alpha of 0.05, and factoring in a 10% patient drop-out, at least 4,303 patients on prasugrel and clopidogrel need to be enrolled, yielding a minimum sample size of 8,606 patients. If it is necessary to extend the window of time beyond 30 June 2013 in order to enroll an adequate number of patients, no protocol amendment will be required.

7 General Considerations

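### The SAP pools patients already on clopidogrel or prasugrel at admission with new starters in a comparison it labels initiation; the bias probably favours prasugrel, but its direction and size cannot be fixed from the documents

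*SAP*

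**What the plan says.** SAP 6.1 (Methods) defines the primary exposure groups as patients "receiving prasugrel or clopidogrel at the time of PCI (i.e. loaded peri-procedurally or currently taking in the absence of a load". Two routes lead into an arm: a load around the procedure, or existing use without one. SAP 5.3, criterion 3, is equally wide: "Treatment with prasugrel or clopidogrel during index hospitalization either prior to, or during the peri-procedural period".

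The protocol is narrower. Its primary objective (3.2.1) concerns patients who started treatment in hospital, and criterion 3 in 3.3.3 opens with "Initiated use of prasugrel or clopidogrel during index hospitalization either prior to, during, or in the peri-procedural period".

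The SAP does not describe its contrast consistently. Section 5.1 says the study evaluates "a treatment strategy initiating prasugrel relative to clopidogrel". The secondary objectives in 4.2 compare patients initiating each drug. Section 6.1 uses initiation for the treatment term in the Cox model and for the dependent variable of the propensity model. Yet the primary objective in 4.1 speaks only of patients treated with one drug or the other, and the clinical outcome tables are organised by therapy at PCI.

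No population of interest in SAP 5.3, and none of the five sensitivity analyses in 6.1, is limited to patients free of a P2Y12 inhibitor at admission. The fifth requires the same drug at PCI and at discharge, which does not touch prior use. Attachment 1 collects clopidogrel, prasugrel and ticagrelor on admission as three separate yes/no fields.

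**The concern.** A patient who has an ACS while on clopidogrel and simply stays on it is not starting a drug. Pooling such patients with new starters gives a contrast that no longer answers the initiation question.

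The two arms are unlikely to be affected equally. SAP 5.1 dates prasugrel's availability to the end of 2009, and the cohort opens on 01 January 2010. Current users are therefore probably mostly on clopidogrel, especially early on. The rationale in both documents says that clopidogrel is given for up to a year after ACS with PCI, and that some patients respond poorly and may be at higher thrombotic risk. If current users carry more MACE risk than new starters, the clopidogrel arm looks worse for a reason unrelated to choosing one drug over the other. They have also already tolerated the drug, which could pull their risk the other way, for bleeding in particular.

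At stake are the composition of the primary cohort and the meaning of the primary hazard ratio.

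**Working it through.** **Inputs from the documents.** SAP 6.8: control 90-day MACE, "the MACE rate at 90 days will be approximately 8.0" per cent; effect, "20% lower than with clopidogrel (hazard ratio 0.80"; 80% power, alpha 0.05, 10% drop-out, 4,303 per arm. Sidedness is not stated; two-sided is assumed here.

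**Inputs assumed, because the documents give none.** Share of current users on clopidogrel, pc = 10% to 30%; on prasugrel, pp = 2% to 5%; their MACE risk relative to new starters, r = 0.8 to 2.0. The middle case is pc = 20%, pp = 2%, r = 1.5.

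**1. The plan's own figure.** Two proportions, 8.0% against 6.4%, give 4,096 per arm before drop-out and 4,096/0.9, about 4,552, after. The stated 4,303 is not reproduced with the 10% drop-out included. That does not bear on this point, so 4,303 is used as stated. With all 4,303 per arm evaluable, power is 81.9%; with 0.9 × 4,303 = 3,873 it is 77.8%.

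**2. Crude effect of mixing.** Apparent HR = true HR × [1 + pp(r − 1)] / [1 + pc(r − 1)].
- Middle case, no true effect: (1 + 0.02 × 0.5)/(1 + 0.20 × 0.5) = 1.01/1.10 = 0.92. With 3,873 per arm, the chance of a significant result favouring prasugrel is about 19%, against a nominal 2.5%.
- Middle case, true HR 0.80: 0.80 × 1.01/1.10 = 0.735.
- r from 1.2 to 2.0: from 1.01/1.02 = 0.99 (pc 10%, pp 5%, r 1.2) to 1.02/1.30 = 0.79 (pc 30%, pp 2%, r 2.0).
- r = 1: 1.00.
- r = 0.8: from 0.99/0.98 = 1.01 to 0.996/0.94 = 1.06, so the sign reverses.

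These are values before adjustment. The primary hazard ratio is stratified by propensity score.

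**3. What adjustment can do.** The propensity model takes age, gender, every baseline covariate that differs at p < 0.05, and consensus variables. Admission clopidogrel, prasugrel and ticagrelor are rows of Table 1. At 20% against 2% with 4,303 per arm, the standard error of the difference is √[(0.16 + 0.0196)/4,303] = 0.0065, so z = 0.18/0.0065, about 28. Admission clopidogrel would enter if the analyst treats it as a baseline covariate. Three gaps remain:
- It is not named in the propensity model or among the listed variables of the covariate-adjusted model, and it is not one of the five variables in the balance check (age, gender, creatinine, hemoglobin, diabetes).
- For a current taker who was not loaded, the admission drug defines the arm. An unloaded home clopidogrel user has no prasugrel counterpart with the same history. This is a lack of overlap, which modelling does not cure.
- Trimming is optional for the primary analysis. The lowest 5% of 8,606 is about 430 patients; 20% of 4,303 is about 861, though some of those would have been re-loaded.

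**4. Cost of restricting.** Removing current users from 4,303 per arm in the middle case leaves 0.80 × 4,303 = 3,442 and 0.98 × 4,303 = 4,217, with two-proportion power of 77.1%. Over the assumed shares the range is 79.5% to 73.5%. With a further 10% loss, power goes from 77.8% to 72.7% (range 75.2% to 69.0%).

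**The case against.** The strongest reply is that the direction is not shown. The documents report no share of current users by arm and no risk for them. Admission P2Y12 use and previous MI and PCI can all enter the propensity model. Matching, the equipoise cohort and the trimmed IPW analysis would thin out patients with extreme scores. If adjustment left a residual r of 1.1, the middle shares would give 1.002/1.02 = 0.98. This stands as a limit on size and sign. It does not answer the lack of overlap for unloaded takers, and those analyses are sensitivity analyses that help only if admission use is in the score.

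A home clopidogrel user who is loaded with prasugrel might be counted as prasugrel, which would move breakthrough cases into that arm, or be excluded as having had both drugs. The SAP does not say which. With 10% current users on prasugrel, 20% on clopidogrel and r = 1.5, the crude HR is 1.05/1.10 = 0.95. This also stands, and it is a reason to write the rule down.

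A reader might infer that a clopidogrel taker loaded with ticagrelor stays in the clopidogrel arm. The text does not settle that: such a patient has had a load, so on a plain reading belongs to neither arm.

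Finally, SAP 4.1 says only treated, so the SAP is internally inconsistent rather than in breach of one clear objective. That is correct, and the inconsistency itself needs resolving.

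**Conclusion.** The mismatch is established from the text. The SAP mixes new and current users, mostly calls the contrast initiation, departs from the protocol's initiation requirement, and plans no analysis that separates the two.

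The bias probably favours prasugrel on MACE. This rests on prasugrel's late market entry and on current users carrying higher risk after adjustment, and the documents do not show the second. The crude null HR of about 0.92, and the range of 0.99 to 0.79, are scenarios under assumed shares and risks; at a relative risk of 0.8 the figures are 1.01 to 1.06. A reader might set these beside the planned HR of 0.80 and infer that mixing alone could produce the expected benefit. The documents do not support that, because the scenarios are unadjusted and the planned estimate is not. Whatever the sign, the mixed cohort does not estimate the effect of starting one drug rather than the other.

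**What to change.** - Align the SAP cohort with the protocol's initiation requirement: restrict the primary analysis to patients with clopidogrel, prasugrel and ticagrelor on admission all coded 0. Deleting only the clause on current use without a load would not do this, because re-loaded current users would remain. This is not a full return to protocol criterion 3, which has no explicit rule on the admission fields and also sets discharge and switching conditions.
- Keep the wider SAP cohort as a sensitivity analysis. At the least, pre-specify the new-user analysis as a sensitivity analysis.
- In the wider cohort, force admission P2Y12 use into the propensity model and add it to the balance check.
- State how home users loaded with a different P2Y12 inhibitor, including ticagrelor, are classified for analysis.
- Make SAP 4.1 agree with 4.2, 5.1 and 6.1, and report current-user shares by arm.

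The cost is SAP wording, since the fields are already collected, and fewer patients, mainly on clopidogrel. Keeping 4,303 new users per arm in the middle case would take 4,303/0.80, about 5,379, clopidogrel patients and 4,303/0.98, about 4,391, prasugrel patients. Without replacement, power falls as shown above. Report the resulting N and power, and settle the rule before any outcome is analysed.

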Procedural ASA	0=no, 1=yes	Indicate if the patient was administered aspirin at any time during index procedure
Procedural Fondaparinux	0=no, 1=yes	Indicate if the patient was administered fondaparinux at any time during index procedure
Procedural LMWH	0=no, 1=yes	Indicate if the patient was administered a lowmolecular heparin at any time during index procedure
Procedural UFH	0=no, 1=yes	Indicate if the patient was administered fondaparinux at any time during index procedure
Procedural Bival	0=no, 1=yes	Indicate if the patient was administered bivalirudin at any time during index procedure
Procedural lib/IIIa	0=no, 1=yes	Indicate if the patient was administered IIb/IIIa inhibitor at any time during index procedure
Clopidogrel loading	0=no, 1=yes	Indicate if the patient was administered a loading dose of clopidogrel

Prasugrel loading	0=no, 1=yes	Indicate if the patient was administered a loading dose of prasugrel
Ticagrelor loading	0=no, 1=yes	Indicate if the patient was administered a loading dose of ticagrelor
Discharge ACE-I or ARB	0=no, 1=yes	At the time of discharge, was the patient prescribed an ACE-Inhibitor (or ARB)
Discharge ASA	0=no, 1=yes	At the time of discharge, was the patient prescribed aspirin
Discharge bbl	0=no, 1=yes	At the time of discharge, was the patient prescribed a beta blocker
Discharge Statin	0=no, 1=yes	At the time of discharge, was the patient prescribed a statin
Discharge Clopidogrel	0=no, 1=yes	At the time of discharge, was the patient prescribed clopidogrel
Discharge Clopidogrel 75 mg	0=no, 1=yes	At the time of discharge, was the patient prescribed clopidogrel 75mg
Discharge Clopidogrel 150 mg	0=no, 1=yes	At the time of discharge, was the patient prescribed clopidogrel 150mg
Discharge Prasugrel	0=no, 1=yes	At the time of discharge, was the patient prescribed prasugrel
Discharge Prasugrel 5mg	0=no, 1=yes	At the time of discharge, was the patient prescribed prasugrel 5mg
Discharge Prasugrel 10mg	0=no, 1=yes	At the time of discharge, was the patient prescribed prasugrel 10mg
Discharge Ticagrelor	0=no, 1=yes	At the time of discharge, was the patient prescribed ticagrelor
Discharge Anticoagulant	0=no, 1=yes	At the time of discharge, was the patient prescribed an anticoagulant (warfarin; LMWH; rivoraxaban)
Multivessel disease	0=no, 1=yes	Value is 1 if number of diseased vessels > 1
Number of lesions treated	##	Total number of lesions treated during the index PCI

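### The SAP excludes peri-procedural switchers whom the protocol admits, defines no window, and lists only undated load flags, so exclusion because of a post-PCI event cannot be ruled out

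*SAP*

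**What the plan says.** SAP 6.1 defines exposure by the drug received at PCI: "loaded peri-procedurally or currently taking in the absence of a load". Patients keep that group "irrespective of medication administered at discharge". The next sentence removes a third set: "Patients administered both medications at the time of PCI will be excluded for any comparative analyses of treatments".

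Protocol 3.3.3, criterion 3, treats such patients differently. It requires that patients "were discharged on the same medication as initiated during the peri-procedural period", and then adds a group: "Patients initiated on 1 agent prior to PCI and then switched to the other agent in the peri-procedural period", with the period given as "prior to, during, or ≤ 3 hours post-procedure) will also be eligible for analysis".

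SAP 5.3, criterion 3, asks for treatment with either drug "either prior to, or during the peri-procedural period (as defined below", but no definition follows anywhere in the SAP. The time of PCI, as used in the exclusion, is not defined either.

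In Attachment 1 of both documents, the clopidogrel entry that would feed the rule reads: "Indicate if the patient was administered a loading dose of clopidogrel". The prasugrel and ticagrelor entries have the same form. All three are 0/1, with no date, time or window. The procedural anticoagulant and aspirin fields nearby are tied to the index procedure, but the loading fields are not.

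**The concern.** Two things look wrong. First, a patient loaded with clopidogrel before PCI and with prasugrel in the laboratory is eligible under the protocol (given the matching discharge drug) and, on the natural reading, excluded under the SAP. The SAP gives no reason for the change.

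Second, the listed data cannot apply the exclusion as worded. Follow-up starts at index PCI (SAP 4.3), and the 90-day MACE analysis includes index-hospital events (SAP 6.1). If a load given after PCI can set the second flag and remove the patient, membership of the primary cohort depends on what happened after time zero. A re-load may follow a bleed or an ischemic event, and both are outcomes here. Propensity strata built from baseline covariates adjust for who was given which drug; they do not restore patients removed because of later events.

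**Working it through.** **Step 1. Apply the rules to four kinds of patient.**

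| Patient | Protocol 3.3.3 | SAP 6.1 as worded | Loading flags (clopidogrel/prasugrel) |
|---|---|---|---|
| A. Clopidogrel load before PCI, prasugrel load in the laboratory, discharged on prasugrel | Eligible | Excluded, on the natural reading | 1/1 |
| B. Taking clopidogrel at admission, loaded only with prasugrel | Appears eligible if discharged on prasugrel | Appears assigned to prasugrel | 0/1 |
| C. Prasugrel load at PCI, clopidogrel load the next day, discharged on clopidogrel | Fails the discharge condition | Stays in the prasugrel group | 1/1 |
| D. As C, but switched without a load | Fails the discharge condition | Stays in the prasugrel group | 0/1 |

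A is the direct conflict between the documents. A and C have the same flags, although the SAP excludes one and keeps the other. The admission fields do not help, and the discharge fields separate A from C only by luck: a patient loaded with clopidogrel before PCI and prasugrel in the laboratory, then discharged on clopidogrel, matches C on every listed antiplatelet field.

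**Step 2. Look for a planned analysis that covers this.** Sensitivity analysis 5 in SAP 6.1 requires the same drug at PCI and discharge, so it does not bring back two-drug patients. The mock tables have no row for the number excluded.

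**Step 3. Ask what the size could be.** The plan gives no figure on this point. The expected 90-day switching rates (at most 10% in Protocol 3.3.1 and SAP 5.1, below 15% in Protocol 3.4.9) do not isolate in-hospital switches or give reasons. From the plan come only the 8.0% clopidogrel rate and the 20% relative reduction (prasugrel 0.080 × 0.80 = 6.4%). Everything else below is assumed.

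If a share g of MACE cases is lost from one arm and nobody else, the observed risk is p(1 − g)/(1 − pg).

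- Lost from clopidogrel, g = 5%: 0.076/0.996 = 7.63%; ratio 0.064/0.0763 = 0.84.
- Lost from clopidogrel, g = 10%: 0.072/0.992 = 7.26%; ratio 0.064/0.0726 = 0.88.
- Lost from prasugrel, g = 5%: 0.0608/0.9968 = 6.10%; ratio 0.0610/0.080 = 0.76.
- Lost from prasugrel, g = 10%: 0.0576/0.9936 = 5.80%; ratio 0.0580/0.080 = 0.72.
- True ratio 1.00, lost from clopidogrel: 0.080/0.0763 = 1.05 and 0.080/0.0726 = 1.10.

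Losing event-free patients pushes the other way. Suppose 1–2% of clopidogrel patients have an early ischemic event, 10–30% of those are re-loaded and lost, and 2% of clopidogrel patients without MACE are also lost. The clopidogrel risk becomes 0.079/0.9806 = 8.06% at the low end and 0.074/0.9756 = 7.59% at the high end. With prasugrel at 1 − 0.92^0.8 = 6.45%, a true hazard ratio of 0.80 reads 0.79 to 0.85, on either side of the truth. Losing 2% of event-free prasugrel patients as well raises prasugrel to 0.0645/(1 − 0.02 × 0.9355) = 6.58%, and the range becomes 0.81 to 0.86.

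For bleeding, assume a true prasugrel rate of 5%, with 15–30% of bleeders and 2–5% of others lost. The observed rate runs from 0.035/(0.035 + 0.95 × 0.98) = 3.6% to 0.0425/(0.0425 + 0.95 × 0.95) = 4.5%.

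**The case against.** The strongest reply is that the SAP's rule, as written, does not select on later events. It covers only drugs given at the time of PCI, and patients stay in their group whatever they receive at discharge. Patient C therefore stays in the prasugrel arm. It is the protocol, through its discharge condition, that would remove C. This stands. A reader might infer that patients switched because of bleeding or ischemia drop out of both arms, favouring prasugrel on bleeding and clopidogrel on MACE. The documents do not say so. It would happen only if the undated flags were used as they stand and the later switch came with a loading dose.

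Nor does the SAP say which fields identify two-drug patients. Section 7.1 promises technical instructions to sites, which are not in the documents, and mock Table 2 lists the two drugs among procedural medications, so the flags may be meant as procedural. That is possible, but the field definitions do not say it, and a strictly in-procedure meaning would miss loads given before PCI.

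It is also fair that excluding dual-exposed patients to obtain mutually exclusive groups is a defensible choice, and that load timing may not be stored: this is retrospective extraction at eight centers (SAP 5.1) without chart review (Protocol 3.5). These points limit what can be asked of sites. They do not supply the missing window, fields or counts.

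**Conclusion.** The point holds as a conflict between documents and a gap in specification. Protocol 3.3.3 and SAP 6.1 disagree on whether peri-procedural switchers are analysed, the SAP refers to a window it does not give, and the listed load fields cannot separate a peri-procedural switch from a later re-load. An outcome-dependent exclusion from the primary comparison therefore cannot be ruled out, and no planned analysis would reveal it.

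The size and direction of any bias are unknown. The figures above rest on assumed loss rates; they show only that modest, selective loss could move the ratio by several hundredths either way.

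Two wider readings should be resisted. The overlap is not every two-drug patient: the protocol also requires the matching discharge drug, and patient B appears assignable under the SAP. The protocol's rule is not the cure either, because its discharge condition selects on events between PCI and discharge.

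**What to change.** 1. Reconcile Protocol 3.3.3 and SAP 6.1 on whether peri-procedural switchers are analysed, and give the reason.
2. Carry one peri-procedural window into the SAP and name the fields that apply it. The rule must also place a patient whose only load falls within the window but after PCI.
3. State that a load given after the window never excludes or reassigns a patient who already has an agent at PCI.
4. Add a timing code to each loading field (before, during, within the window after, later) where sites hold it.
5. Report the number of two-drug patients excluded, by first drug where known, with their 90-day MACE and bleeding counts.
6. Add a sensitivity analysis of 90-day MACE and bleeding that keeps them. Assign by the agent at PCI where timing exists; otherwise assign all to prasugrel, then all to clopidogrel. Call these scenarios, not bounds: placing patients with events in one arm and those without in the other would be more extreme.
7. Do not bring the protocol's discharge-drug condition back into the primary cohort.

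The cost is SAP wording, one code per loading field where available, a count in the tables and a few model runs. The downside is some exposure misclassification where timing is missing.
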